
Endpoints (Continued):
	
Pharmacokinetics: The PK profile of REL-1017 25 mg and 50 mg will be evaluated on Day 1 through Day 7, Day 8, Day 9, and Day 14 where the data allow:
 
 • Maximum observed plasma concentration (C_{max}) • Time to maximum observed plasma concentration (T_{max}) • Area under the plasma concentration-time curve from time zero until the dosing interval of 24 hours (AUC_{tau}) • Area under the plasma concentration-time curve from time zero until the last quantifiable time point (AUC_{0-last}) on Day 7 • Area under the plasma concentration-time curve from time zero to infinity (AUC_{0-inf}) • Apparent termination elimination rate constant (λ_z) • Apparent terminal elimination half-life ($t_{1/2}$) • Attainment of steady state • Steady state clearance (C_{SS}/F) • Volume of distribution at steady state (V_{SS}/F) • Accumulation ratios based on minimum observed plasma concentration (C_{min}), C_{max}, and AUC_{tau} 
Efficacy: The following assessments will be conducted to evaluate efficacy:
 
 • Change from Baseline (Day 1) to the End of the Dosing Period (EDP, Day 7) on the Montgomery-Asberg Depression Rating Scale (MADRS) • Change from Baseline (Day 1) to EDP (Day 7) on the Symptoms of Depression Questionnaire (SDQ) • Change from Baseline (Day 1) to EDP (Day 7) on the Clinical Global Impressions of Severity (CGI-S) scale. • Change from Baseline (Day 2) to EDP (Day 7) on The Clinical Global Impressions of Improvement (CGI-I) scale will be measured at pre-dose on Day 2, post-dose on Day 4 and Day 7 within 3 hours of dosing, and on Day 14. 
The timing of each assessment is detailed in the Time and Events Schedule (Table 1).

Study Design:
	
A Phase 2a, Multicenter, Randomized, Double-Blind, Placebo-Controlled, 3-Arm Study to Assess the Safety, Tolerability, PK Profile, and Symptom Response of a 7-Day Dosing with REL-1017 25 mg QD and 50 mg QD as Adjunctive Therapy in the Treatment of Patients Diagnosed with MDD

Investigational Product:
	
REL-1017 (d-Methadone) 25 mg, 50 mg, 75 mg and 100 mg Powder Formulation

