Statistical Data Analysis (Continued):	
Pharmacokinetics (Continued):
 
Concentrations below the limit of quantification (BLQ) will be set to zero for the generation of summary statistics for concentrations and the generation of mean concentration time plots.
 
For the calculation of the PK parameters, concentration-time data will be treated as follows: BLQ concentrations prior to the first quantifiable concentration will be set to zero; BLQ concentrations after the first quantifiable concentration will be treated as missing; and pre-dose sampling times relative to dosing will be set to zero.
 
Descriptive statistics, including number of patients, mean, SD, geometric mean, geometric CV, minimum, maximum, and median will be calculated for all REL-1017 PK parameters except T_{max} or $t_{1/2}$. The T_{max} data will be summarized with number of patients, minimum, maximum, and median. The $t_{1/2}$ data will be summarized with number of patients, mean, SD, minimum, maximum, and median.
 
Efficacy:
 
The depressive symptom changes associated with 7 days of daily dosing with REL-1017 25 mg and 50 mg will be measured using the MADRS, SDQ, and CGI-S. The MADRS, SDQ, and CGI-S will be conducted pre-dose at Baseline (Day 1) and on Day 2; post-dose on Day 4 and Day 7 within 3 hours of dosing; and at EOP (Day 14). The CGI-I will be measured at pre-dose on Day 2, post-dose on Day 4 and Day 7 within 3 hours of dosing, and on Day 14.
 
The change from Baseline in each parameter on Day 7 will be compared among treatment groups (Placebo, REL-1017 25 mg, and REL-1017 50 mg) using a MMRM (Mixed Model of Repeated Measurement) with treatment group, stratification (concomitant antidepressant drug) factor, visit (Day 2, Day 4, and Day 7), interaction between treatment and visit as independent variables, and Baseline endpoint as a covariate. Least square (LS) means with standard errors (SEs), differences in LS means with standard errors (SEs), 90% confidence intervals (Cis) for the difference in LS means, and corresponding P-values will be presented.
 
Actual values, absolute change, and percent change from Baseline will be summarized by treatment and all visits.
 
The assumptions of normality may be evaluated using the Shapiro-Wilks test. If the assumptions of normality are not satisfied, the ranked change and ranked Baseline may replace the change and Baseline in the above mixed model as a sensitivity analysis.

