
^g Patients will be asked to abstain from alcohol for 24 hours prior to Screening, 24 hours prior to Check-in to the CRU, while in the CRU, and 24 hours prior to the Day 14 visit.

^h Sites should submit specific Screening information (detailed in the MGH CTNI manual) within 72 hours after the Screening Visit for review by the external medical team prior to proceeding to Check-in.

ⁱ The patient's prescribed antidepressant will be administered by site personnel while the patient is confined to the study unit.

^j A whole blood sample for DNA isolation will be collected from all patients in this study for potential pharmacogenetic analysis of genes that may affect the PK of d-methadone. Pharmacogenetic analysis will be performed only in cases where patients exhibit abnormal PK results. This analysis will be restricted to the evaluation of genes that may be involved in the PK of d-methadone (e.g., drug metabolism, disposition, elimination). One 4 mL whole blood sample for DNA isolation will be collected on Day 1 from each patient. Samples will be collected and shipped according to the site's standard operating procedures (SOPs) and instructions from the Sponsor and/or pharmacogenetic laboratory. The samples will be stored in a secure space with adequate measures to protect patient confidentiality. The samples will be retained while research on d-methadone (REL-1017) continues, but not longer than 20 years.

^k MADRS, SDQ, and CGI-S will be conducted pre-dose on Day 1 and Day 2; post-dose on Day 4 and Day 7 within 3 hours of dosing; and on Day 14. The CGI-I will be conducted at pre-dose on Day 2; post-dose on Day 4 and Day 7 within 3 hours of dosing; and on Day 14.

^l 4-Item PSRS and CADSS will be measured at 30 to 60 minutes pre-dose on Day 1, 2 hours post-dose on Day 1, 2 hours post-dose on Day 7, and prior to Discharge on Day 9.

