2.2 Secondary Objectives

The secondary objectives of this study are:

2.2.1 Pharmacokinetics:

The PK objective will characterize the PK profile of 25 mg and 50 mg of REL-1017 (d-methadone) as adjunctive treatment in patients with MDD. The PK profile of REL-1017 25 mg and 50 mg will be evaluated on Day 1 through Day 7, Day 8, Day 9, and Day 14 where the data allow:

- Maximum observed plasma concentration (C_{max})
- Time to maximum observed plasma concentration (T_{max})
- Area under the plasma concentration-time curve from time zero until the dosing interval of 24 hours (AUC_{tau})
- Area under the plasma concentration-time curve from time zero until the last quantifiable time point (AUC_{0-last}) on Day 7
- Area under the plasma concentration-time curve from time zero to infinity (AUC_{0-inf})
- Apparent termination elimination rate constant (λ_z)
- Apparent terminal elimination half-life ($t_{1/2}$)

- Attainment of steady state
- Steady state clearance (C_{SS}/F)
- Volume of distribution at steady state (V_{SS}/F)
- Accumulation ratios based on minimum observed plasma concentration (C_{min}), C_{max} , and AUC_{τ}

2.2.2 Efficacy:

The efficacy of 7 days of daily dosing with REL-1017 25 mg and 50 mg will be measured with the following efficacy endpoints:

- Change from Baseline (Day 1) to End of the Dosing Period (EDP, Day 7) on the Montgomery-Asberg Depression Rating Scale (MADRS) with measurements made pre-dose on Day 1 and Day 2; post-dose on Day 4 and Day 7 within 3 hours of dosing; and on Day 14;
- Change from Baseline (Day 1) to EDP (Day 7) on the Symptoms of Depression Questionnaire (SDQ) with measurements made pre-dose on Day 1 and Day 2; post-dose on Day 4 and Day 7 within 3 hours of dosing; and on Day 14; and,
- Change from Baseline (Day 1) to EDP (Day 7) on the Clinical Global Impressions of Severity (CGI-S) with measurements made pre-dose on Day 1 and Day 2; post-dose on Day 4 and Day 7 within 3 hours of dosing; and on Day 14.
- Evaluation of Clinical Global Impressions of Improvement (CGI-I) total score on Day 7 (post-dose), as well as CGI-I scores on Days 2 (pre-dose), 4 (post-dose), and 14.

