8.1.3.3 Secondary Objectives: Efficacy of REL-1017

The efficacy of 7 days of daily dosing with REL-1017 25 mg and 50 mg as measured by the following efficacy endpoints:

- Change from Baseline (Day 1) to EDP (Day 7) on the MADRS with measurements made pre-dose on Day 1 and Day 2; post-dose on Day 4 and Day 7 within 3 hours of dosing; and on Day 14;
- Change from Baseline (Day 1) to EDP (Day 7) on the SDQ with measurements made pre-dose on Day 1 and Day 2; post-dose on Day 4 and Day 7 within 3 hours of dosing; and on Day 14;

- Change from Baseline (Day 1) to EDP (Day 7) on the CGI-S with measurements made pre-dose on Day 1 and Day 2; post-dose on Day 4 and Day 7 within 3 hours of dosing; and on Day 14.
- Evaluation of CGI-I total score on Day 7 (post-dose), as well as CGI-I scores on Days 2 (pre-dose), 4 (post-dose), and 14.

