8.1.4.5 Analysis of Efficacy Assessments

The depressive symptom changes associated with 7 days of daily dosing with REL-1017 25 mg and 50 mg will be measured using the MADRS, SDQ, and CGI-S. The MADRS, SDQ, and CGI-S will be conducted pre-dose at Baseline (Day 1) and on Day 2; post-dose on Day 4 and Day 7 within 3 hours of dosing; and at EOP (Day 14). The CGI-I will be administered pre-dose on Day 2; post-dose on Day 4 and Day 7 within 3 hours of dosing; and at EOP (Day 14).

The change from Baseline in each parameter on Day 7 will be compared among treatment groups (Placebo, REL-1017 25 mg, and REL-1017 50 mg) using a mixed model of repeated measurement with treatment group, stratification (concomitant antidepressant drug) factor, visit (Day 2, Day 4, and Day 7), interaction between treatment and visit as independent variables, and Baseline endpoint as a covariate. Least square (LS) means with standard errors, differences in LS means with standard errors, 90% confidence intervals for the difference in LS means, and corresponding P-values will be presented.

Actual values, absolute change, and percent change from Baseline will be summarized by treatment and all visits.

The assumptions of normality may be evaluated using the Shapiro-Wilks test. If the assumptions of normality are not satisfied, the ranked change and ranked Baseline may replace the change and Baseline in the above mixed model as a sensitivity analysis.

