11.10 Clinical Global Impressions (CGI) Scale

CGI Source Document for Baseline CGI Administration

Clinical Global Impressions of Severity (CGI-S)

Severity	
Considering your total clinical experience with this particular population, how mentally ill is the patient at this time?	 1 - Normal, not at all ill  2 - Borderline mentally ill  3 - Mildly ill  4 - Moderately ill  5 - Markedly ill  6 - Severely ill  7 - Among the most extremely ill patients

CGI Source Document for Post-Baseline CGI Administrations (Days 2, 4, 7, 14)

Clinical Global Impressions of Severity (CGI-S)

Severity	
Considering your total clinical experience with this particular population, how mentally ill is the patient at this time?	 1 - Normal, not at all ill  2 - Borderline mentally ill  3 - Mildly ill  4 - Moderately ill  5 - Markedly ill  6 - Severely ill  7 - Among the most extremely ill patients

Clinical Global Impressions of Improvement (CGI-I)

Improvement	
Rate total improvement whether or not in your judgment it is due entirely to drug treatment. Compared to his condition at admission to the project, how much has he changed?	 1 - Very much improved  2 - Much improved  3 - Minimally improved  4 - No change  5 - Minimally worse  6 - Much worse  7 - Very much worse

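### The Synopsis measures CGI-I as change from a post-dose Day 2 'baseline', against the Day 7 score in Sections 2.2.2 and 8.1.3.3, and the stated mixed model, if applied to CGI-I, needs a baseline that CGI-I lacks

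*Combined protocol and SAP*

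**What the plan says.** **Endpoint.** The Synopsis, under Endpoints (Efficacy), gives "Change from Baseline (Day 2) to EDP (Day 7) on The Clinical Global Impressions of Improvement (CGI-I) scale" and then runs on into a list of visits. Section 2.2.2 has "Evaluation of Clinical Global Impressions of Improvement (CGI-I) total score on Day 7 (post-dose", and Section 8.1.3.3 has "Evaluation of CGI-I total score on Day 7 (post-dose". Both of these add the Day 2, 4 and 14 scores and neither subtracts anything.

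**Schedule.** Table 1, footnote k: "The CGI-I will be conducted at pre-dose on Day 2; post-dose on Day 4 and Day 7 within 3 hours of dosing", and again on Day 14. There is no Day 1 CGI-I. MADRS, SDQ and CGI-S are all rated on Day 1 before dosing.

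**Scale.** Appendix 11.10 places CGI-I on a form headed "CGI Source Document for Post-Baseline CGI Administrations (Days 2, 4, 7, 14", and the item reads "Compared to his condition at admission to the project, how much has he changed". Section 6.6.2.2 gives seven categories, with 4 meaning no change.

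**Model.** The Synopsis and Section 8.1.4.5 describe one efficacy model: "The change from Baseline in each parameter on Day 7 will be compared among treatment groups". It is a repeated-measures mixed model with Days 2, 4 and 7 as response visits and the Baseline value as covariate. Section 8.1.4.5 opens by saying that symptom change "will be measured using the MADRS, SDQ, and CGI-S" and gives only visit times for CGI-I. Section 8.1.7, however, lists CGI-I among the four measures whose missing data a mixed model will address. Section 8.1.2 leaves complete analysis details to an SAP that was not supplied.

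**The concern.** Two current parts of the protocol define the same endpoint as different quantities. The Synopsis version uses as its reference a rating made after treatment has started, so it subtracts whatever treatment effect already exists on Day 2. An early effect matters to this programme: Section 1.3.1 cites a 2-hour onset for ketamine, another NMDA antagonist.

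The analysis text does not resolve the conflict. If the stated model is meant to cover CGI-I, it requires a Baseline value that is never collected, and the Synopsis wording offers an analyst a convenient but wrong one. Section 8.1.4.5 plans 90% confidence intervals and P-values, and Section 8.2 plans effect sizes for the efficacy measures. A reported CGI-I effect would therefore depend on which definition was followed.

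**Working it through.** The protocol states no figure for CGI-I to reproduce. The check compares the definitions and then asks whether the stated model can be fitted under each.

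**1. Is Day 2 before treatment?** No. The Synopsis dose schedule starts dosing on Day 1, and the Day 2 rating is made before the second dose, hence after the first. A footnote to Table 1 ties Baseline to Day 1 and pre-dose assessment. Appendix 11.10 puts Day 2 on the post-Baseline form. Section 8.1.4.5 itself uses Day 2 as a response visit.

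**2. How many CGI-I ratings precede the first dose?** From Table 1 and footnote k:

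| Measure | Days rated | Ratings before first dose |
|---|---|---|
| CGI-S | 1, 2, 4, 7, 14 | 1 |
| CGI-I | 2, 4, 7, 14 | 0 |

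**3. What does each definition estimate?** Let d2 and d7 be the active-minus-placebo differences in mean CGI-I on Days 2 and 7; negative values favour active.

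- Sections 2.2.2 and 8.1.3.3: contrast = d7.
- Synopsis, as an unadjusted change: contrast = d7 − d2.
- Synopsis, as a change adjusted for the Day 2 score: contrast = d7 − b·d2, where b is the within-arm slope of Day 7 on Day 2. With equal SDs, b equals their correlation.

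The documents give no CGI-I values. For illustration only, assume d7 = −0.8 and, for the adjusted version, a correlation of 0.6:

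| Assumed d2 | Day 7 score | Change from Day 2 | Change adjusted for Day 2 |
|---|---|---|---|
| 0 | −0.8 | −0.8 − 0 = −0.8 | −0.8 − 0.6 × 0 = −0.80 |
| −0.4 | −0.8 | −0.8 + 0.4 = −0.4 | −0.8 + 0.6 × 0.4 = −0.56 |
| −0.8 | −0.8 | −0.8 + 0.8 = 0.0 | −0.8 + 0.6 × 0.8 = −0.32 |

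The three columns agree only when d2 = 0.

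**4. Can the stated mixed model be fitted to CGI-I?**

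- *Baseline = Day 1.* CGI-I has no Day 1 value, so neither the response (change from Baseline) nor the covariate exists.
- *Baseline = Day 2.* The Day 2 response is Day 2 minus Day 2, which is 0 for every patient, yet Day 2 is one of the three response visits. The protocol names no covariance structure. Assuming an unstructured one, SD 1 and correlation 0.6 at each visit, the covariance matrix of the Day 2, 4 and 7 changes has rows (0, 0, 0), (0, 0.8, 0.4) and (0, 0.4, 0.8). Its rank is 2 and its determinant 0, so the three-visit model fails unless Day 2 is dropped.

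The absolute and percent change summaries and the ranked sensitivity analysis in Section 8.1.4.5 need the same missing Baseline. Summaries of actual values do not.

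**The case against.** The strongest reply is that this is an editorial slip that nobody would act on. The Synopsis bullet is a broken sentence: its subject is a change score and its predicate a visit schedule. Without the first ten words it is a complete scheduling sentence, which is how the Amendment 3 table of changes records it. The objectives and the endpoint-definitions section agree on the Day 7 score. A Day 2 or a Day 1 baseline would also break the model at programming, so the problem would probably be noticed. Most of this stands and it limits the weight of the point, but the bullet is current text that defines an endpoint.

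The second reply is that the model is left to the SAP. This stands in part. A reader might infer that the protocol has no usable analysis for CGI-I. The documents do not support that. Section 8.1.7 names a mixed model without requiring change from Baseline, so a model on observed scores would be consistent with it. The opening of Section 8.1.4.5 can be read as leaving CGI-I to descriptive reporting, which would be acceptable for an exploratory measure. What remains is conditional: if the model in Section 8.1.4.5 is meant to cover CGI-I, it does not fit as written.

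A reader might also infer from the ketamine citation that a Day 2 effect of REL-1017 is expected and will be lost. That citation concerns another drug. It shows why an early effect would matter, not that one exists.

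**Conclusion.** The point holds as a correction to be made before unblinding. The Synopsis contradicts Sections 2.2.2 and 8.1.3.3 on the CGI-I endpoint. If followed, it would replace d7 with d7 − d2, or with a partly reduced version if adjusted for the Day 2 score. This rests on the schedule, the CGI form and an algebraic identity, not on assumed effect sizes. The amount removed cannot be known from the documents and is zero if there is no Day 2 difference.

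That the mixed model cannot be fitted is firm for a Day 1 baseline. For a Day 2 baseline it also assumes an unstructured covariance with Day 2 kept as a response visit. In both cases it depends on the model being meant for CGI-I, which the wording of Sections 8.1.4.5 and 8.1.7 suggests and the SAP may settle.

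The scope is one of four efficacy measures, exploratory, with about 20 patients per arm in a study that Section 8.2 says is not powered for signal detection. The documents do not show that any reported result would be biased, since two body sections already give a sound definition.

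**What to change.** 1. In the Synopsis efficacy endpoints, delete the first ten words of the CGI-I bullet (everything before the name of the scale), and use the Day 7 CGI-I score throughout, as in Sections 2.2.2 and 8.1.3.3.

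2. In Section 8.1.4.5 or the SAP, state that any mixed model for CGI-I takes the observed scores at Days 2, 4 and 7 as response, with treatment, stratum, visit and treatment-by-visit interaction and no CGI-I baseline term, and that change and percent change from Baseline are not computed for CGI-I. Make the matching Synopsis analysis text consistent.

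Two choices remain for the SAP author. Day 1 CGI-S may be added as a severity covariate, and an ordinal or responder analysis could be used for a seven-category scale. Whichever is chosen should be written down before unblinding.

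The cost is ten words deleted and about two sentences added. No new data are needed: CGI-I on Days 2, 4, 7 and 14 and CGI-S on Day 1 are already scheduled.
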